Schizophrenia is a severe mental illness that affects millions of people worldwide. The illness is often associated with social impairments, including limitations in verbal and non-verbal behavior, initiating conversations, and social motivation. People with schizophrenia often report a desire to socialize but expend less effort in the actual behavior and set fewer socially-related goals than others. While diminished social motivation is not fully understood, past research suggests a reduced ability to connect past, pleasurable experiences with current states, resulting in reduced effort for social connection in people with schizophrenia. Because this reduced effort for social connection may cause people with schizophrenia to have difficulty obtaining relationships they desire, it is important to focus on factors that are modifiable, such as social skills and motivational deficits. Interventions that target these impairments usually take place at mental health clinics, but there is a growing recognition that people with schizophrenia need assistance with these skills outside of a clinical setting.

Findings from an ongoing study (i.e., Aims 1 and 2 of the larger grant; (NIMH# R21MH111501-01, IRB protocol #4394) will inform development of a pilot intervention study examining the impact of this mobile application on social functioning over time. We will employ a two-site study to test the application in a group of 30 persons with schizophrenia over a 60-day period. We will measure social functioning at baseline, intervention termination, and 90-day follow-up using clinician administered interviews and self-report questionnaires. We hypothesize that levels of social functioning will increase significantly from baseline to post-intervention and follow-up, and that these increases will be accompanied by increased self-reported social motivation using periodic measures incorporated into the mobile application.

SECTION H: RESEARCH METHODS AND ACTIVITIES (Check all that apply)

\boxtimes	Collection of audio, video, digital, or image recordings
	Biological samples → Complete Biological Samples Form:
	http://www.bu.edu/researchsupport/compliance/human-subjects/
	Examples: blood, hair, cheek swab, urine, tears, saliva, etc.
	Collection of data that may be sensitive and if disclosed could put subjects at risk for
	legal or social harms.
	Examples: Illegal behaviors, HIV status, psychiatric illness, information related to
	sexual behaviors, etc.

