We will exclude participants with a current (past 6 months) substance use disorder, which will be determined by administration of the SCID-5, self-reported current suicidal ideation with intent and/or a plan (assessed using attached instrument; i.e., "High" risk), or self-reported diagnosis of a current/ongoing neurological disorder (i.e. not managed with medication). We will exclude participants who have been hospitalized in the past month for mental health reasons or for life threatening physical conditions (such as stroke or heart attack). Potential participants who have a guardian and cannot sign consent independently will be excluded.

SECTION J: RECRUITMENT

Provide a summary of the recruitment process, including who will recruit, when and where recruitment will occur, and how subjects will be identified

Note: Submit any recruitment materials such as advertisements, brochures, flyers, letters/e-mails, scripts, etc. Please submit these materials as separate documents in either Word or PDF format.

Participants with schizophrenia or schizoaffective disorder will be outpatients recruited from clinics within the Boston and San Francisco community, including the BU Center for Psychiatric Rehabilitation (CPR). Flyers will be posted throughout the CPR and around the community as well. The investigators have extensive contacts in this community. Potentially eligible consumers will also be identified through informing clinicians and recovery center instructors at each site about the study and eligibility criteria for participation. We will provide clinicians with study flyers. We will also verbally brief all partnering clinicians on the overall study aims and goals. They will have access to the consent form for review Referrals to the study will be made by either consumers' providers or by recovery center instructors (at CPR). When a referral is made, the consumer's provider/instructor will meet with the consumer to briefly explain the project. If the consumer is potentially interested in participating in the project, the referrer will arrange for the consumer to contact the Project Coordinator by phone or in person, who will ask the screening questions (see attached phone screen form). Eligible consumers who express interest in participating in the study and are able to correctly answer questions about the project (demonstrating their comprehension) will attend an in-person

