Following our current usability testing (anticipated completion: August 2018), we will employ a two-site study to test the MASS application in a total of 30 persons (we will recruit up to 50 people to account for attrition, ending up with complete data on 15 persons per site) with schizophrenia or schizoaffective disorder over a 60-day period. We will measure social functioning at baseline, intervention termination, and 90-day post-intervention follow-up using the Social Functioning Scale (SFS) and the Quality of Life Scale (QLS). Social cognition and preference for personal space will be measured with the Stop Distance Paradigm. We will also measure symptoms and cognitive function with the Brief Psychiatric Rating Scale (BPRS) or the Wide Range Achievement Test (WRAT), the Clinical Assessment Interview for Negative Symptoms (CAINS), Penn Emotion Recognition Task (ER-40) and the Brief Assessment of Cognition Schizophrenia (BACS). Self-report measures to assess theory of motivation and social skills will also be administered. Self-report measures and the ER-40 will be administered through Qualtrics. Demographic information will be collected through a custom questionnaire and the Structured Clinical Interview for DSM-5 [SCID-5]). Participant satisfaction questionnaire will also be administered at termination and a subset of the satisfaction questions will be administered at follow up.

Procedures

Baseline Assessment. After providing informed consent, participants will complete diagnostic and clinical evaluations at the Center for Psychiatric Rehabilitation or in the [name] or [name] laboratories. The assessment procedures will involve a total of 4 hours for the completion of clinical interviews, demographics questionnaires, cognitive/behavioral tests, and community functioning measures, conducted over 1-2 days as needed by participants. At the conclusion of the assessment, the participant will be issued a mobile phone and trained on its use. They will identify a social goal and work with study staff to lay out sub-goals and steps necessary to achieve them—this goal will be programmed into the mobile app based on a pre-defined set of available goal prototypes. Participants will be oriented to all application components during this visit. They will also be given instructions to watch the social skill video clips within the app.

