Quality of Life Scale (QLS)	Social Functioning	B, T, F
Brief Psychiatric Rating Scale	Psychiatric Symptoms	B, T, F
(BPRS)		
Clinical Assessment Interview for	Psychiatric Symptoms	B, T, F
Negative Symptoms (CAINS)		
Stop Distance Paradigm	Social Cognition	B, T, F
Penn Emotion Recognition Task	Social Cognition	В
(ER-40)		
Brief Assessment of Cognition	Neurocognition	В
Schizophrenia (BACS)		
Wide Range Achievement Test	Neurocognition	F
(WRAT)		
Self-reports: Implicit Theory of	Social Cognition	В
Motivation (TOM), Implicit		
Theory of Social Skills (TOSS)		
Self-Reports: Birchwood Social	Social Functioning	B, T, F
Functioning Scale		
Satisfaction Questionnaire.	N/A	T, F
Demographics	N/A	В

^{*}B = Baseline; T = Termination; F = Follow-up

Analyses

Primary analyses will examine changes in social functioning across the study period using multivariate models accounting for covariates of interest (e.g., demographics, cognition). This mobile application is both an intervention and assessment tool. Thus, during the intervention we will be able to measure additional targets of interest, social motivation and functioning, using the EMA reports of positive affect in anticipation of social interactions, as well as reports of actual engagement in interactions, throughout the intervention period.

This study is a within-subject experimental design. Consistent with an experimental therapeutics approach, our primary goal is to identify change within the treatment targets (social anticipatory pleasure and presence of social interaction). Accounting for up to 20% attrition, we aim to recruit 50 participants, allowing for 20 participants to drop out/not meet criteria and still leave adequate power for primary analyses. Our primary aims are to pilot test the intervention to determine feasibility and efficacy in the treatment targets (social skills and motivation) and outcome (social functioning).

SECTION M: RISKS

Describe any expected risks to subjects. Consider physical, psychological, social, political, legal, economic, or other risks that are related to the study.

There are some risks associated with participation in the study. The primary risks involve loss of confidentiality associated with pilot testing of the mobile application. It is also possible that some participants may feel some frustration when participating in the MASS application. Participants may also feel discomfort answering questions about their health in the clinical assessments.

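### The primary aim of determining efficacy claims more than a single-arm before-after design can support; the aim and the permitted conclusion should be reworded.

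*Combined protocol and SAP*

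**What the plan says.** All references are to the combined protocol and SAP.

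- **Aim (Section L, Analyses).** "Our primary aims are to pilot test the intervention to determine feasibility and efficacy in the treatment targets (social skills and motivation"). The sentence goes on to name social functioning as the outcome.
- **Design label (Section L, Analyses).** "This study is a within-subject experimental design".
- **Who gets what (Section L, Phase II).** "we will employ a two-site study to test the MASS application in a total of 30 persons". One group at two sites is described, and all of them use the app for 60 days.
- **When outcomes are measured (Section L, Phase II).** "We will measure social functioning at baseline, intervention termination, and 90-day post-intervention follow-up". There is one baseline.
- **What is compared (Section L, Analyses).** "Primary analyses will examine changes in social functioning across the study period using multivariate models accounting for covariates of interest". The covariates given as examples are demographics and cognition.
- **EMA measures of the targets (Section L, Analyses).** "during the intervention we will be able to measure additional targets of interest, social motivation and functioning". No EMA collection before the app starts is stated.
- **Hypothesis (Section G, Study Summary).** "We hypothesize that levels of social functioning will increase significantly from baseline to post-intervention and follow-up".
- **Staff contact (Section L, Procedures).** Staff work out goals and steps with each participant at baseline, telephone them about the skills videos in the first days, and make further calls according to EMA adherence over the 60 days.
- **Eligibility (Section I).** "We will exclude participants who have been hospitalized in the past month for mental health reasons". There is no entry threshold for low social functioning.

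**The concern.** Efficacy is a claim about what the app causes: how participants fare with it compared with how they would have fared without it. The plan observes only the first of these. A before-after change contains any effect of the app together with everything else that moves scores over the 60-day intervention and the 90 days after it. The documents supply no comparison group, waiting period, repeated baseline, randomised order or external benchmark with which to separate them.

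At stake is what the trial may conclude. Efficacy stands as a primary aim, and no section says that an uncontrolled change cannot be attributed to the app. A reader of the plan therefore has no stated limit on what a positive result means. A test of no change from baseline controls the error rate for the statement that scores changed. It does not control the error rate for the statement that the app worked.

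**Working it through.** **1. Can any feature of the design supply the missing comparison?**

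| Feature | Location | Does it isolate the app? |
|---|---|---|
| Two sites | Section L, Phase II | No. Both sites deliver the app. |
| Covariate adjustment | Section L, Analyses | No. It compares participants with one another; it does not show their course without the app. |
| 90-day follow-up | Section L, Phase II; Section G | No. It is not a withdrawal phase, because the hypothesis predicts improvement there too. |
| EMA reports | Section L, Analyses | No. They are described only during the intervention, so even change from an app-free state is undefined for them. |

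**2. Which rival explanations do the documents support?**

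- *Time.* Supported in general, since 60 days pass before termination and a further 90 before follow-up. Recovery after discharge is a narrower possibility: Section I excludes admissions in the past month only, and how many recently discharged people would enter is unknown.
- *Repeat testing.* Supported. The Measures table lists the SFS, QLS, BPRS and CAINS at all three time points.
- *Staff contact.* Supported if the question is what the app does. If the intervention is the app plus this contact, it is a component rather than a rival. The plan does not say which.
- *Regression to the mean.* Weak. With no low-functioning threshold, it could arise only through referral or self-selection.

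**3. How large could the effect be?** The plan gives no figure to reproduce here. Power is called adequate, with no alpha, effect size or SD, and no drift or correlation is stated. What follows is an illustration.

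From the plan: n = 30 with complete data. Assumed: a paired t-test, two-sided alpha 0.05, no app effect, upward drift d in units of the score SD (equal at both visits), and visit-to-visit correlation r.

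The SD of change is √(2(1 − r)) score SDs, so the standardised drift is dz = d/√(2(1 − r)). The noncentrality is dz·√30, and the critical value on 29 df is 2.045. The chance of a significant improvement is the upper tail of the noncentral t beyond 2.045.

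| d | r | dz | dz·√30 | Chance of significant improvement |
|---|---|---|---|---|
| 0 | any | 0 | 0 | 2.5% |
| 0.2 | 0.5 | 0.200 | 1.095 | 18% |
| 0.2 | 0.7 | 0.258 | 1.414 | 28% |
| 0.2 | 0.8 | 0.316 | 1.732 | 39% |
| 0.3 | 0.5 | 0.300 | 1.643 | 36% |
| 0.3 | 0.7 | 0.387 | 2.121 | 54% |
| 0.3 | 0.8 | 0.474 | 2.598 | 71% |

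A downward drift works the other way: at −0.2 SD the chance is below 0.2% for each of these correlations.

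**4. Would a control arm be the remedy at this size?** No. Splitting the 30 completers into 15 and 15 raises the effect detectable at 80% power from about 0.53 to about 1.06 SD of change (two-sided 0.05). Power at 0.53 SD would be about 29%. A single arm is reasonable for feasibility; the claim attached to it is what needs to change.

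**The case against.** The strongest reply is that the plan is more modest than one sentence suggests. It calls itself a pilot throughout and puts feasibility first. In Section L (Analyses) it also gives its primary goal as finding change in the treatment targets, and Section N promises no known direct benefit. Within-subject is accurate, and the experimental label is tied to an experimental therapeutics approach, so part of the dispute is terminology. Much of the staff contact appears under the heading for the mobile intervention and can be read as part of the package. The calculation assumes both drift and correlation, and a paired t-test stands in for the planned multivariate models.

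Most of this stands, and it limits the point. Three stronger readings are tempting and should not be drawn:

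- *That the plan makes a significant rise its efficacy conclusion.* It contains no such rule, no alpha and no success criterion. The hypothesis in Section G is about change and is compatible with the design. That a positive result would be over-read is an inference from the aim, not something the plan says.
- *That regression to the mean is built into recruitment.* Eligibility gives it no mechanism beyond referral or self-selection, and the one-month hospitalisation exclusion works partly against early recovery.
- *That later score against own baseline is the only comparison.* The EMA reports during the intervention are also planned, although they too are uncontrolled.

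What the reply does not remove is the efficacy aim itself. The pilot label and the modest goal sit beside it without qualifying it.

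**Conclusion.** The point holds. A primary aim claims an inference that the design cannot deliver, and no section restricts how change may be interpreted. This is wrong as written, and a should-fix: it affects what may be concluded, not how the study is run.

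The structural conclusion needs no numerical assumption. Its size cannot be fixed from the documents. If scores drifted up by 0.2 SD with no app effect, a significant improvement would appear in 18-39% of trials for correlations of 0.5 to 0.8, against 2.5% nominal in that direction. With zero drift the nominal rate is kept, and with downward drift the chance falls below it. None of these percentages is an estimate for this trial.

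**What to change.** Change Section L (Analyses) only:

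1. Restate the primary aim as *determine feasibility and estimate within-person change* in the targets and the outcome, dropping efficacy.
2. Describe the design as *single-arm pre-post*.
3. Make the reported result the mean change with its 95% CI, taken from the models already planned.
4. Add one sentence: *a significant change will not by itself be taken as evidence of the app's efficacy*.

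It would help to say there whether goal setting and staff calls belong to the intervention under test. The Section G hypothesis can stay, since it concerns change.

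The cost is wording. Sample size, visits, measures and models are untouched, and no control arm is asked for. The downside is a less favourable stated aim.
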